- Randomization to the different arms in the pre-malignant stomach group will be made by the computer software after all the variables have been fulfilled:

Subsequent Endoscopic and biopsies follow-up

- In all patient's complete gastroscopy first with White light and then with virtual CE will be made;
- Suspicious lesion with dysplasia/cancer will be biopsied 1-2 fragments in a different vial; if an irregular area of mucosa (pattern C) with no clearly defined lesion then 1-2 guided biopsies fragments will be taken and sent in a different vial;

- EGGIM will be calculated according to what previous described ^{17 18};
- If EGGIM 0 (no endoscopically apparent IM) biopsies will be made in antrum, incisura and corpus according to Sydney-Houston protocol;
- If EGGIM 1 or more guided biopsies of suspicious areas of IM should be made replacing the random biopsies in that particular area (e.g. if IM in lower curvature but not in the greater curvature of the antrum then you should do targeted biopsies in the lower curvature and random in the greater curvature; if IM in both antrum areas then you should only do targeted biopsies; in each case at least two antrum fragments should be taken and biopsies should be sent in the same antrum vial);
- Antrum, incisura and corpus fragments should be sent in 3 separate vials;

Subsequent clinical evaluation and follow-up

- All patients that complete 2nd endoscopy and biopsy protocol will be evaluated 2 to 6 weeks after in a clinical consultation.
- Endoscopic and histologic data of the second/third procedure will be fulfilled on an online database.
- If no lesion and no irregular area were seen and random biopsies do not present dysplasia then the patient maintain the previous defined endoscopic follow-up (1 or 3 years).
- If an irregular area was seen (with no clearly defined lesion) but guided biopsies negative for atypia/dysplasia then the patient maintain the previous defined endoscopic follow-up (1 or 3 years).
- If an irregular area was seen (with no clearly defined lesion) and guided biopsies present atypia/dysplasia or if random biopsies of any gastric area present dysplasia then outcome 1 was reached and patient follow-up should respect current guidelines (endoscopy 3-6 months if high-grade and 6-12 months if low-grade dysplasia) ¹⁹.

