- If a suspicious superficial lesion was seen and biopsies present atypia, dysplasia or cancer then staging and resection of the lesion will be made; Only after resection and/or complete staging, the outcome will be assumed according to the following:
 1. Outcome 1: lesion presenting only dysplasia (low or high grade)
 2. Outcome 2: lesion presenting carcinoma

- Outcome 2.1 intramucosal carcinoma with low-risk criteria (“curative” criteria)
- Outcome 2.2 submucosal, diffuse type or intramucosal carcinoma with high-risk criteria (“non-curative” criteria)
- Outcome 2.3: advanced cancer (more than previous, implying impossibility of endoscopic resection)

End of study

- The study is designed for 6 years, when all data will be analyzed and results presented;
- Patient follow-up will be completed at 6 years or when one of the outcomes is reached;
- Continuation of the study after 6 years is possible and predictable and will be decided after data analysis.

Subprojects

[figure not shown]
- In order to clarify the natural history of other specific situations not considered in the main project two additional groups of patients will be followed-up prospectively:
 1. Patients with persistent Hp gastritis and non-premalignant stomach (Patients with EGGIM 0 and OLGA 0/I/II; and patients with EGGIM 1-3 with biopsies negative for IM (OLGIM 0) and OLGA not higher than II);
 - We suggest endoscopic follow-up in 3 (if family history of gastric cancer) to 6 years (if no family history of gastric cancer) in these group of patients;
 - We predict 12 years follow-up of these patients (two to four follow-up endoscopies);
 - Data analysis after 12 years follow-up;
 2. Patients that in follow-up reach outcome 1 (dysplasia) but with no clearly defined lesion for resection (small irregular areas with dysplasia) or random biopsies with dysplasia; Natural history of these patients is not clearly defined since in previous studies many of them might already present a lesion at the time of diagnosis.

- We suggest endoscopic follow-up accordingly to guidelines, 3-6 months if high-grade dysplasia and 6-12 months if low-grade dysplasia;
 - If after two negative endoscopies with no dysplasia/lesion, then we suggest endoscopy in 1 (if family history) to 3 years (if no family history).
- In both of these subprojects the endoscopic and biopsies protocol will be the same of the main project.

Sample size calculation (SUPREME I)

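### Outcome 1 rule omits dysplasia found in IM-targeted biopsies when nothing suspicious is seen, so incidence by EGGIM stage can be biased

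*Protocol*

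**What the plan says.** **Biopsies at follow-up** (Protocol, Methods, Subsequent Endoscopic and biopsies follow-up). Three kinds are described:

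- fragments from a suspicious lesion or irregular area, sent in their own vial;
- guided fragments from areas that look like IM, which replace the random fragments in that area;
- random fragments elsewhere.

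For the antrum the instruction goes further: "if IM in both antrum areas then you should only do targeted biopsies". Targeted and random antral fragments go into one antrum vial.

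**Outcome and follow-up rules** (Subsequent clinical evaluation and follow-up). A patient stays on schedule under this rule: "If no lesion and no irregular area were seen and random biopsies do not present dysplasia then the patient maintain the previous defined endoscopic follow-up". A second continuation rule concerns irregular areas: "If an irregular area was seen (with no clearly defined lesion) but guided biopsies negative for atypia/dysplasia then the patient maintain". Outcome 1 has two limbs. The first is "If an irregular area was seen (with no clearly defined lesion) and guided biopsies present atypia/dysplasia"; the second is "or if random biopsies of any gastric area present dysplasia then outcome 1 was reached". A further rule covers visible lesions: "If a suspicious superficial lesion was seen and biopsies present atypia, dysplasia or cancer then staging and resection of the lesion will be made".

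**Subproject 2** (Subprojects) takes in patients who reach outcome 1 "but with no clearly defined lesion for resection (small irregular areas with dysplasia) or random biopsies with dysplasia".

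**Elsewhere.** Sample size calculation (SUPREME I) describes outcome 1 simply as dysplasia. Primary aim 1 is the incidence of dysplasia/cancer by endoscopic and histological stage. Secondary aim 1 is the same risk by EGGIM stage.

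**The concern.** The biopsy section treats IM-targeted fragments as a type distinct from random ones and requires them. The outcome rules written a few lines later give that type no classification unless a lesion or irregular area was also seen. The same histology is therefore outcome 1 if it comes from a random fragment and no outcome if it comes from an IM-targeted one.

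This matters because biopsy type is set by EGGIM, and EGGIM is the exposure in secondary aim 1 and part of the staging in primary aim 1. If invisible dysplasia can count only from random fragments, the chance of recording it falls as the stage rises. Outcome ascertainment then depends on exposure, and the bias runs against the gradient that the study expects to show. Subproject 2, which exists to follow dysplasia without a resectable lesion, would lose the same patients.

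**Working it through.** **Step 1. One case against each rule.** The patient has EGGIM of at least 1, no lesion and no irregular area seen, and dysplasia in an IM-targeted fragment only.

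| Rule | Requires | Met? |
|---|---|---|
| Outcome 1, first limb | irregular area seen | No |
| Outcome 1, second limb | dysplasia in random biopsies | No; the fragment replaced a random one |
| Visible-lesion rule | suspicious lesion seen | No |
| Second continuation rule | irregular area seen | No |
| First continuation rule | no lesion, no irregular area, random biopsies free of dysplasia | Yes, on its wording |
| Subproject 2 | irregular area or random biopsies with dysplasia | No |

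The only rule met is the one that keeps the schedule unchanged and records no outcome.

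**Step 2. How this varies with EGGIM.** The baseline protocol sets a minimum of 2 antrum + 2 corpus + 1 incisura = 5 fragments at EGGIM 0, and follow-up refers to the same Sydney-Houston scheme. At EGGIM 0 all 5 are random, and dysplasia in any of them is outcome 1. With IM in every sampled area, 0 of 5 are random, and invisible dysplasia cannot be outcome 1 on the wording. Intermediate stages lie between.

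**Step 3. Can the distinction be applied?** Where one antral area has IM and the other does not, both fragment types go in the antrum vial. A vial-level report of dysplasia does not show which type carried it. In these patients the rule cannot be applied reliably even by a site that wants to follow it to the letter.

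**Step 4. The plan's own figure.** The sample size uses outcome 2 rates of p1 = 0.01 and p2 = 0.05, alpha 0.05 (taken as two-sided; sidedness is not stated) and power 90%. With the mean rate at 0.03:

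n per group = [1.960 × √(2 × 0.03 × 0.97) + 1.282 × √(0.01 × 0.99 + 0.05 × 0.95)]² / 0.04² = 381 after rounding up.

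The protocol gives 380, so its figure reproduces. Outcome 1 does not enter the formula, so the sample size does not depend on this point.

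**Step 5. Illustration of size (assumption).** The protocol gives no share q of outcome 1 events that would be found only in IM-targeted fragments with nothing suspicious seen. Its expected outcome 1 rates are 5% (yearly arm) and 1% (three-year arm), or 380 × 0.05 = 19 and 380 × 0.01 = 3.8 events. Under literal application, events lost = 380 × rate × q:

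| Assumed q | Yearly arm: lost of 19; rate left | Three-year arm: lost of 3.8; rate left |
|---|---|---|
| 10% | 1.9; 4.5% | 0.4; 0.9% |
| 25% | 4.8; 3.75% | 1.0; 0.75% |
| 50% | 9.5; 2.5% | 1.9; 0.5% |

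These values of q have no source in the protocol. The true share could be below 10%, and if sites count such cases anyway the loss is nil.

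**The case against.** The best defence is that random biopsies was meant as shorthand for the whole antrum, incisura and corpus set, in contrast to fragments from an area suspicious for dysplasia. Several places support this:

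- Secondary aim 4 ties random biopsies to dysplasia that has no suggestive endoscopic appearance.
- Only lesion and irregular-area fragments get their own vial.
- The sample size section equates outcome 1 with dysplasia.
- The Discussion says the natural history will rest on guided as well as random biopsies.
- On the narrow sense, the first continuation rule would have no biopsy to test in a patient with IM everywhere; its condition would be true only because it is empty.

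This is plausible as intent and it stands to that extent. But no section states it, the biopsy section uses the two terms as alternatives, and 15 confirmed centres may read the rule differently. It is also fair that follow-up histology is entered in the online database, so such cases might be reclassified at analysis; that would still need a stated definition.

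Three stronger readings are tempting and are not supported.

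- **That dysplasia is certain to be undercounted.** This depends on literal or inconsistent application, which the protocol permits but does not prove.
- **That the rules collide** when an irregular area is biopsy-negative and a random fragment elsewhere is dysplastic. The random-biopsy limb covers any gastric area, and the End of study section closes a patient's follow-up once an outcome is reached, so outcome 1 naturally takes precedence.
- **That the randomised comparison is undermined.** It is powered on outcome 2 and both arms use the same rules. The only route is indirect: a patient whose dysplasia is not recorded stays in follow-up and could later be counted as outcome 2.

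**Conclusion.** The point holds as a defect in the outcome definition. Followed as written, the outcome 1 rule and subproject 2 leave out dysplasia from a biopsy type that the protocol itself requires, and the omission grows with EGGIM. If sites apply the wording literally, or differ in how they apply it, dysplasia is undercounted in the higher stages and the stage-specific incidence in primary aim 1 and secondary aim 1 is biased against the expected gradient. The direction follows from the text; the size cannot be computed from the protocol, and the event counts above rest on an assumed share. The sample size for outcome 2 stands. It should be corrected before outcomes are classified, because it concerns a primary aim and wording alone resolves it.

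**What to change.** - **Outcome classification.** In the outcome 1 definition and in subproject 2, state that dysplasia in any antrum, incisura or corpus biopsy counts, whether random or IM-targeted. This also removes the need to know which fragment in a shared antrum vial was which.
- **Follow-up wording.** The continuation rules under Subsequent clinical evaluation and follow-up, and the related text under Subprojects, must then be reconciled with that definition. The interval for such patients is for the investigators to settle; this review proposes none.

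**Cost:** a wording amendment, with no new procedures, data or patients.

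### Outcome 1 is defined inconsistently: atypia without dysplasia counts as an event in an irregular area, but not in random biopsies or a visible lesion

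*Protocol*

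**What the plan says.** All references are to the Protocol.

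*Subsequent clinical evaluation and follow-up* sets rules by type of finding:

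- **Irregular area without a defined lesion, and random biopsies.** One sentence covers both: if "guided biopsies present atypia/dysplasia or if random biopsies of any gastric area present dysplasia then outcome 1 was reached". The intervals that follow in that sentence are given for high-grade and low-grade dysplasia only.
- **Irregular area, negative case.** The assigned schedule continues if "guided biopsies negative for atypia/dysplasia then the patient maintain the previous defined endoscopic follow-up". Both terms must be absent.
- **Nothing seen.** The assigned schedule continues if "random biopsies do not present dysplasia then the patient maintain the previous defined endoscopic follow-up". Atypia is not mentioned.
- **Visible lesion.** If "biopsies present atypia, dysplasia or cancer then staging and resection of the lesion will be made". An outcome is assigned only after resection or complete staging, and the list then reads "Outcome 1: lesion presenting only dysplasia (low or high grade"). Outcome 2 is worded for a lesion that contains carcinoma. The branches without a lesion do not mention carcinoma.

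*Subprojects* describes a group of patients who "reach outcome 1 (dysplasia) but with no clearly defined lesion for resection (small irregular areas with dysplasia"), or who have dysplasia on random biopsies. *Sample size calculation (SUPREME I)* also labels outcome 1 as dysplasia and outcome 2 as cancer.

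*End of study* adds: "Patient follow-up will be completed at 6 years or when one of the outcomes is reached".

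**The concern.** Whether the same histology is an event depends on how the tissue was sampled. Atypia alone is an outcome in an irregular area. In a random fragment it is not, and in a visible lesion it prompts staging and resection but becomes an outcome only if dysplasia or carcinoma is then found.

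Three things are at stake:

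- **Primary aim 1** is the incidence of dysplasia/cancer. A literal reading adds non-dysplastic findings to it.
- **Outcome 1 by arm.** The rule operates at each examination, and the arms differ in their number of examinations. Extra events would not fall equally on the two arms.
- **Completion of follow-up.** Main-study follow-up is completed at any outcome. An atypia-only patient would be an event with no grade and no stated interval.

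This is not a detail that can wait for an analysis plan. The protocol itself states the event rule, 15 centres have to apply it, and main-study follow-up that was completed on the literal reading cannot be restored at the analysis.

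**Working it through.** **1. Is atypia/dysplasia one entity?** The irregular-area rule joins the words with a slash, which could mean a single finding. The visible-lesion rule in the same section lists atypia, dysplasia and cancer as three alternatives. The irregular-area sentence itself drops atypia when it turns to random biopsies. The text therefore does not support reading the two words as synonyms.

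**2. How is outcome 1 described elsewhere?** The outcome list, the subproject and the sample size section all say dysplasia. The subproject does so for the very group at issue, irregular areas without a resectable lesion. The post-outcome intervals also cover dysplasia only. The irregular-area rule is the only place where atypia counts.

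**3. The plan's own sample size.** Inputs from *Sample size calculation*: outcome 2 at 6 years of 1% versus 5%, alpha 0.05, power 90%. With a two-sided pooled test of two proportions,

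n = [1.960 × √(2 × 0.03 × 0.97) + 1.2816 × √(0.01 × 0.99 + 0.05 × 0.95)]² / 0.04² = 380.1.

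This is 381 per group when rounded up, against the stated 380. Power at 380 is 0.8999, so the figure reproduces. It rests on outcome 2 alone.

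**4. Examinations per arm.** *Patient inclusion in the surveillance trial and randomization* gives 12 to 16 months and 32 to 40 months. Over 72 months, 72/12 = 6 and 72/16 = 4.5, so about 4 to 6 examinations. For the other arm, 72/32 = 2.25 and 72/40 = 1.8, so about 2.

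**5. Atypia-only events.** The documents give no rate. Assume a chance q per endoscopy of an irregular area with atypia only, constant and independent between examinations. Over k examinations the probability is 1 − (1 − q)^k.

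| q (assumed) | k = 6 | k = 4 | k = 2 | Per 380, 6 vs 2 |
|---|---|---|---|---|
| 0.25% | 1.49% | 1.00% | 0.50% | 5.7 vs 1.9 |
| 0.5% | 2.96% | 1.99% | 1.00% | 11.3 vs 3.8 |
| 1% | 5.85% | 3.94% | 1.99% | 22.2 vs 7.6 |

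The ratio of yearly to 3-yearly is about 2.9 to 3.0 with 6 examinations and about 2.0 with 4. The plan expects outcome 1 in 5% versus 1%, which is 0.05 × 380 = 19 versus 0.01 × 380 = 3.8 patients.

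**6. Any outcome.** The plan expects 6% in both arms. Adding atypia-only events gives 1 − 0.94 × (1 − q)^k. At q = 0.25% this is 7.4% versus 6.5%. At q = 1% it is 11.5% versus 7.9%.

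**7. Outcome 2.** Spread the planned outcome 2 risk p evenly over the k examinations, and remove patients at an atypia-only event that is independent of cancer risk. The observed risk is (p/k) × Σ(1 − q)^i, for i from 0 to k − 1. At q = 1%:

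- yearly: (0.01/6) × 5.85 = 0.98%
- 3-yearly: (0.05/2) × 1.99 = 4.98%

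Power at 380 per group stays at about 0.90.

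**The case against.** The strongest reply is that this is a slip of wording. Three other places call outcome 1 dysplasia, and the intervals in the same sentence fit dysplasia only, so centres may well apply it that way. That is plausible, and it shows which way the text leans. It does not settle the matter, because the irregular-area rule uses the wider term in both its positive and its negative branch.

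A second reply is that atypia in a targeted irregular area may deliberately be treated differently from atypia in a random fragment. That could justify different follow-up. It would not explain why an incidence of dysplasia/cancer should include it.

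The objections to the size largely stand. The atypia rate is assumed. At 1% per endoscopy, atypia-only events in the yearly arm (5.9%) would nearly equal the plan's entire 6-year incidence of 6%. If atypia persists between examinations, the 3-yearly arm would find more at each one and the ratio would shrink.

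Three stronger readings are tempting, and the documents do not support them:

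- **That the powered comparison is compromised.** Under independence it barely changes (step 7). If atypia marks higher cancer risk the effect could be larger, but the documents give no figure for this.
- **That later cancer goes unobserved.** What is completed is main-study follow-up. Patients with outcome 1 continue with endoscopy under guidelines, and those without a resectable lesion are followed in a subproject with the same endoscopy and biopsy protocol. Atypia-only patients have no clear place there, because its text names dysplasia.
- **That dysplasia in fragments targeted at intestinal metaplasia has no class.** These fragments replace random ones in their area, and the random-biopsy rule extends to any gastric area, so this is over-literal.

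**Conclusion.** The definition of outcome 1 is internally inconsistent and should be corrected. As written, atypia without dysplasia in an irregular area is counted in the incidence of dysplasia/cancer and completes main-study follow-up, against every other description of outcome 1 in the protocol.

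The imbalance between arms is an inference from the examination schedule: up to about 2 to 3 times as many such events in the yearly arm, given an equal and independent chance per examination. Its absolute size is unknown. The range of 1.5% to 5.9% versus 0.5% to 2.0% rests on an assumed 0.25% to 1% per endoscopy and on 6 versus 2 examinations. Against a planned 5% versus 1%, even the lower end would be visible in the outcome 1 counts.

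The harm falls on primary aim 1 and on outcome 1 by arm. No material effect on the outcome 2 comparison is shown.

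**What to change.** Reconcile the irregular-area rule with the outcome list, the subproject text and the sample size section. Define the endpoint once, by the worst histology in any specimen, however it was sampled:

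- outcome 1: low-grade or high-grade dysplasia
- outcome 2: carcinoma, including carcinoma found without a visible lesion, which the present wording does not place

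Record atypia-only findings as a separate variable that is not counted as outcome 1 in the analysis. The attachment listing the database variables is not among the documents seen, so such a field may already exist.

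This change concerns only how the endpoint is counted. The outcome 1 rule also moves the patient to a different follow-up, so the passages on how atypia-only patients are followed must be reconciled too, and that is for the investigators.

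The cost is one definition in the protocol and at most one database field. The outcome 1 count may be slightly lower. The 380 per group is unchanged, because it rests on outcome 2.

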- We predict that the shorter interval of follow-up (1 year) will allow the diagnosis of lesions in a less advanced stage (more outcome 1 – dysplasia - and lower or inexistent outcome 2 - cancer);
- We anticipate that 1% of patients at risk per year will develop one of the outcomes (6% at the end of the 6-year follow-up) and that most of outcomes 2 (cancer) will be reached in the longer period of follow-up (3 year) for a 6-year total of 1% outcome 2 in the 1-year follow-up group (and 5% outcome 1) and 5% in the 3-year follow-up group (and 1% outcome 1);
- For showing this 4% incidence difference between the two groups (4% more incidence of outcome 2 in the 3-year follow-up group) at the end of follow-up (6 years) with an alpha level of 0.05 and a power of 90% we calculate that at least 760 patients will have to be randomized (380 per group of follow-up);
- Predicting 20% of lost to follow-up and/or necessity to anticipate endoscopy in some patients (because of symptoms/clinical reasons) we calculate that additional 152 patients will have to be randomized for a **total of 912 patients (456 per group of follow-up)**;
- We predict participation of at least 15 centers and, so, **each center must include at least 62 patients in the randomization**;
- Since inclusion of the patients in the randomization trial will only be known after an initial endoscopic and histologic evaluation, and predicting that only 20-25% of the patients will have criteria for inclusion in SUPREME I **each center must include at least 300 patients in the study (these patients will be included in SUPREME II and III)**.

Flowchart (SUPREME I, II AND III)

DISCUSSION/EXPECTED RESULTS

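### SUPREME I follow-up ends at dysplasia, so a cancer found afterwards has no stated route into the randomised comparison of 6-year cancer incidence

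*Protocol*

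**What the plan says.** **Stop rule.** Protocol, *End of study*: "Patient follow-up will be completed at 6 years or when one of the outcomes is reached". The outcomes are defined under *Subsequent clinical evaluation and follow-up*: outcome 1 is dysplasia and outcome 2 is carcinoma. Reaching either one completes follow-up.

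**Endpoint and size.** Protocol, *Sample size calculation (SUPREME I)*. The opening bullet predicts that yearly endoscopy will find lesions at an earlier stage, with more dysplasia and little or no cancer. The overall event rate is put as "1% of patients at risk per year will develop one of the outcomes (6% at the end of the 6-year follow-up"), the same for both arms. It is divided as "1% outcome 2 in the 1-year follow-up group (and 5% outcome 1) and 5% in the 3-year follow-up group (and 1% outcome 1"). The sample size is then set for "showing this 4% incidence difference between the two groups (4% more incidence of outcome 2 in the 3-year follow-up group") at 6 years, with alpha 0.05, 90% power and 380 patients per arm. Adding 20% for losses gives 912 (456 per arm).

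**After outcome 1.**
- Dysplasia without a defined lesion: the patient moves to guideline follow-up and into the second subproject. The subprojects are introduced as covering the "natural history of other specific situations not considered in the main project two additional groups of patients will be followed-up prospectively". The schedule there reads "We suggest endoscopic follow-up accordingly to guidelines, 3-6 months if high-grade dysplasia and 6-12 months if low-grade dysplasia", and no duration is given. The first subproject, by contrast, has one: "We predict 12 years follow-up of these patients".
- Dysplasia in a defined lesion: the outcome is assigned only once the lesion has been resected and/or fully staged. No later study follow-up is described.

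**The concern.** The event that ends follow-up is related to the event being counted, and by the protocol's own forecast it occurs five times as often in the yearly arm as in the 3-year arm. Once a patient has dysplasia, main-project follow-up is complete, and the protocol does not say whether a cancer found later, but still within 6 years, is counted in the randomised comparison.

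Two questions are therefore left unseparated. One is the stage at which disease is first detected under each interval. The other is how many patients have cancer by year 6 under each interval. The sample size section forecasts rates that fit the first and uses the vocabulary of the second. A primary aim is to define the best follow-up, and a reader of the results will want the second answer as well. Nor can later cancers be taken as absent: for dysplasia without a defined lesion, the protocol says "Natural history of these patients is not clearly defined since in previous studies many of them might already present a lesion".

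**Working it through.** **1. Reproduce the protocol's figure.** Inputs from the sample size section: 5% v 1%, alpha 0.05 (taken as two-sided), power 90%. Pooled two-proportion formula:

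n = [1.960 × √(2 × 0.03 × 0.97) + 1.282 × √(0.05 × 0.95 + 0.01 × 0.99)]² / 0.04² = 380.1 per arm.

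The protocol states 380, so the sizing stands for 1% v 5%.

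**2. Which endpoint do the rates describe?** Yearly arm: 5% + 1% = 6%. 3-year arm: 1% + 5% = 6%. Each arm exhausts the single 6% total, so each patient is counted once. That is outcome 2 as *first* outcome.

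**3. How often does outcome 1 end follow-up?**

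| | Yearly | 3-year | Total |
|---|---|---|---|
| Outcome 1, 380 per arm | 380 × 0.05 = 19 | 380 × 0.01 = 3.8 | 22.8 of 760 |
| Outcome 1, 456 per arm | 456 × 0.05 = 22.8 | 456 × 0.01 = 4.6 | 27.4 of 912 |
| Outcome 2 counted, 380 per arm | 380 × 0.01 = 3.8 | 380 × 0.05 = 19 | |

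**4. What if some outcome 1 patients have cancer found by year 6?** Let gY and gT be the fractions in the yearly and 3-year arms. The documents give neither, so these are assumptions.

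- Any cancer by year 6, yearly: 1 + 5gY %
- Any cancer by year 6, 3-year: 5 + gT %
- Difference: 4 − 5gY + gT points

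| gY | gT | Difference (points) |
|---|---|---|
| 0 | 0 | 4.00 |
| 5% | 0 / 5% / 10% | 3.75 / 3.80 / 3.85 |
| 10% | 0 / 10% / 20% | 3.50 / 3.60 / 3.70 |

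At gY = 10% and 380 per arm, the uncounted cancers are 19 × 0.10 = 1.9 in the yearly arm. In the 3-year arm they are 0 to 0.8 (3.8 × 0 to 3.8 × 0.20).

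**5. When would the 4 points not be an overstatement?** Only when gT ≥ 5gY; at gY = 10% that means gT of at least 50%. One mechanism that could be checked is time left to month 72, assuming outcome 1 is found equally often at each planned round within the protocol's windows.

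- Yearly arm: mean 2.5 years (rounds every 12 months) to 2.7 years (every 16 months).
- 3-year arm: 1.5 years (every 36 months) or 2.0 years (every 32 months). With rounds every 40 months it is 1.3 or 2.7 years, depending on whether the month-80 round is counted as the last one.

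The 3-year to yearly ratio is thus about 0.5 (1.3/2.7) to 1.1 (2.7/2.5), far from 5. This covers time left only; a different mix of dysplasia grades between the arms is not addressed.

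**The case against.** The best defence is that the design is a stage-at-detection trial and is consistent as such. The opening bullet of the sample size section says so in substance, the 6% is split additively, and ending follow-up at the first outcome fits both. The imbalance in dysplasia is then the predicted benefit of yearly endoscopy. **This stands.** A reader might infer that the stop rule contradicts the endpoint or that 380 per arm is wrong. The documents support neither.

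Second, patients with dysplasia and no defined lesion are to be followed prospectively in the second subproject, under the same endoscopy and biopsy protocol as the main project. **This also stands in part.** A reader might infer that their later cancers are lost and that no analysis plan could retrieve them, which goes too far. Those cancers may well be observed, but outside the main project, on a suggested schedule with no stated duration. Patients with a resected outcome 1 lesion have no described follow-up at all. For them, cancer in the specimen is already outcome 2, so only later cancers are at issue.

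Third, no sentence says that later cancers are excluded; this is inferred from the stop rule, the additive split and the subproject wording. An analysis plan, not available here, might address how they are analysed. **Fair, but limited:** an analysis plan can use only what the protocol has collected.

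Fourth, the size rests on an assumed fraction, and the yearly arm keeps its advantage in every case shown. **Agreed.** A reader might go on to infer that the trial is underpowered, since at 10% in both arms the power for any cancer at 380 per arm would be 79%. That applies an assumed fraction to an endpoint the protocol did not size, so it is no criticism of the 380.

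**Conclusion.** The point holds as a limit on what the randomised result can show. Follow-up ends at the first outcome of any kind; outcome 1 is expected to end it in about 19 v 4 patients (23 v 5 at 456 per arm); and nothing in the protocol brings a later cancer back into the comparison. The first-outcome result is valid for stage at first detection. As a statement about 6-year cancer incidence, it overstates the gain from yearly surveillance if some outcome 1 patients have cancer found by year 6, unless that fraction is at least five times as high in the 3-year arm.

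The illustrated loss is 0.15 to 0.5 of the 4 points for gY of 5% to 10%, and negligible near zero. These fractions are assumptions; the documents give none. The point does not show that the yearly arm's advantage is an artefact. It merits correction because the remedy is small and bears on the primary aim of defining the best follow-up.

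**What to change.** 1. *End of study*: keep outcome 1 as a first-outcome endpoint, but make it non-terminal for data collection in SUPREME I. Clinical care stays as it is.
2. Record any outcome 2 up to year 6 in every randomised patient, by arm. Link the second subproject's records to the main database through year 6, and add patients with a resected outcome 1 lesion, whom that subproject does not cover.
3. *Sample size calculation (SUPREME I)*: state that 1% v 5% and the 90% power refer to outcome 2 as first outcome.
4. Report any outcome 2 by 6 years, by randomised arm, alongside the first-outcome result.

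**Cost:** continued data entry to year 6 for about 27 of 912 patients (about 23 of 760). The any-cancer analysis may show a smaller difference and is not separately powered, which should be stated. No increase in sample size is asked for.
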